Efficacy of Laser Debridement on Pain and
Bacterial Load in Chronic Wounds
(NCT03182582)

Study Protocol

November 5, 2015

[name], Principal Investigator
Stanford University
Stanford, California 94305

PROTOCOL SYNOPSIS

Title	The assessment of bio-burden reduction and procedural pain after chronic ulcer debridement.
Sponsor	Sciton, Inc. [name] [contact]
Clinical site	Stanford Advanced Wound Care Center [name] [contact]
Rationale	Chronic ulcers are a significant source of morbidity and pain. Biofilms are present in all chronic ulcer types. Additional methods for safe, effective, and tolerable chronic ulcer bed debridement are needed.
Study design	Randomized-controlled cross over, open label study
Primary objective	To determine the efficacy of the reduction of bioburden in chronic ulcers after laser and sharp debridement.
Secondary objectives	To determine the tolerability of laser and sharp debridement of chronic ulcers.
Number of subjects	Twenty
Subject selection inclusion criteria	
 • Aged eighteen years or older • Having a non-healing chronic ulcer of any etiology present for at least four weeks • Willing and able to adhere to protocol requirements • Signed Informed Consent Form prior to any study related procedure
Subject selection exclusion criteria	
 • Any unstable medical condition • Documented medical history of any significant disease or condition • Documented medical history of immunosuppression • Receiving dialysis • Having osteomyelitis • Pregnancy • Participation in another clinical study involving ulcers within thirty days prior to enrollment
Control treatment	Sharp (scalpel or curette) debridement with standard of care
Test treatment	Laser debridement with standard of care
Duration of subject participation	Subjects will be enrolled in the study for two weeks
Duration of study	The total duration of the study is expected to be six weeks. Recruitment and enrollment: up to four weeks Treatment: two weeks
Prohibited concomitant medications	Current topical or systemic antibiotic therapy
Efficacy evaluations	Significant bioburden reduction as determined by quantitative polymerase chain reaction (PCR) analysis after the debridement procedures.

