Primary endpoint	Comparison of the two treatment modalities to reduce bioburden as determined by quantitative polymerase chain reaction (PCR) analysis, DNA sequencing.
Secondary endpoint	Comparison of the procedural pain from the two treatment modalities as determined by subject reported visual analog scale (VAS) pain scores. Comparison of the procedural bleeding from the two treatment modalities as determined by physician assessment. Procedural bleeding
Other evaluations	Overall subject satisfaction from the two treatment modalities.
Safety evaluations	Incidence of adverse events.
Planned interim analysis	Serious adverse events will be audited by the study team on an ongoing basis throughout the study duration.
Primary statistical analysis plan	Treatment effectiveness will be assessed by a two-sample t-test comparing the evaluation criterion at the two study intervals.
Rationale for number of subjects	This is a pilot study to determine treatment feasibility and efficacy.

SUBJECT INCLUSION CRITERIA

A subject will be eligible for inclusion in this study if ALL of the following criteria apply:

[figure not shown]
- Aged eighteen years or older
- Having an ulcer of any etiology
- Has signed the informed consent form prior to any study protocol related procedure
- Willing and able to adhere to protocol requirements

SUBJECT EXCLUSION CRITERIA

The subject will not be eligible for study inclusion if ANY of the following criteria apply:

- Any unstable medical condition that would cause the study treatment to be detrimental to the subject, as judged by the Principle Investigator
- Documented medical history of significant cardiac, pulmonary, gastrointestinal, endocrine (*other than Diabetes Mellitus type 1 or 2*), metabolic, neurological, hepatic or nephrologic disease would impede the subject's participation, as judged by the Principle Investigator
- Documented medical history of immunosuppression, immune deficiency disorder, or currently using immunosuppressive medications
- Having clinical presentation of active osteomyelitis
- Pregnancy or lactation
- Participation in another clinical study involving ulcers within thirty days prior to enrollment

STUDY DESIGN

ULCER DEBRIDEMENT

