Efficacy of Laser Debridement on Pain and Bacterial Load in Chronic Wounds (NCT03182582)

Statistical Analysis Plan

February 6, 2018

[name], Principal Investigator
Stanford University
Stanford, California 94305

Methods:

This is a prospective, randomized, controlled, crossover clinical trial, entailing two groups: 1) one group receiving a single laser debridement session first, followed by a single sharp debridement session one week later; 2) the other group receiving a single sharp debridement session first, followed by a single laser debridement session one week later. Analysis variables include pain during debridement, pre- and post-debridement wound sizes, pre- and post-debridement bacterial loads, and patient preference.

Statistical Analysis:

The a priori power analysis presumes a 50% reduction in patient-reported pain. A sample size of 22 patients would be required to achieve 80% power, using a two-tailed test with $\alpha = 0.05$. Descriptive analyses include means (standard deviation). A paired t-test was planned to evaluate continuous data, and the 3x2 Fisher's exact test was planned to analyze categorical data. For all data analyses performed in the study, $p < 0.05$ is considered statistically significant.

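### The SAP sizes the trial on pain (22 patients) and tests everything at p < 0.05 without carrying forward the protocol's primary endpoint, bioburden, or mentioning its planned 20 subjects

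*SAP*

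**What the plan says.** **Protocol (November 2015), Synopsis.** The number of subjects is twenty, and the only reason given is that this is a pilot. The primary objective is "To determine the efficacy of the reduction of bioburden in chronic ulcers after laser and sharp debridement". The primary endpoint is "Comparison of the two treatment modalities to reduce bioburden as determined by quantitative polymerase chain reaction (PCR) analysis", with DNA sequencing also named. Pain appears under Secondary endpoint: "Comparison of the procedural pain from the two treatment modalities as determined by subject reported visual analog scale (VAS) pain scores". The primary analysis is a two-sample t-test. No significance level, power or effect size is stated.

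**SAP (February 2018), Statistical Analysis.** "The a priori power analysis presumes a 50% reduction in patient-reported pain". On that basis, "A sample size of 22 patients would be required to achieve 80% power", two-sided at 0.05. "A paired t-test was planned to evaluate continuous data", and Fisher's exact test is to be used for categorical data. "For all data analyses performed in the study, $p < 0.05$ is considered statistically significant".

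**SAP, Methods.** "Analysis variables include pain during debridement, pre- and post-debridement wound sizes, pre- and post-debridement bacterial loads, and patient preference". None of these is labelled primary or secondary. The SAP does not mention the twenty, and neither document explains how 20 and 22 relate.

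**The concern.** The later document, which sets the tests and the significance rule, gives its only power statement for an endpoint that the protocol ranks as secondary. It lists pain first, ranks nothing, and treats any p-value below 0.05 as significant. Read on its own, it would let a significant pain result stand as the main finding while the protocol's primary comparison, bioburden, was null, and nothing in the SAP would mark the change. The ranking matters more because the trial is open label and pain is self-reported, whereas bioburden is measured by PCR.

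A second and smaller matter is that the two documents give different numbers of patients with no link between them. If the protocol's number still governs, it is below what the SAP says its own pain assumption needs.

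**Working it through.** **1. Can the 22 be reproduced?** The inputs from the SAP are a 50% reduction, 80% power, two-sided α = 0.05 and a paired t-test. The missing input is the SD. Let r be the SD of the within-patient pain difference divided by mean pain under sharp debridement. The standardised paired difference is then d = 0.5/r, and

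power(n, d) = P(|T| > t with n−1 df at 0.975), where T is noncentral t with n−1 df and noncentrality d√n.

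The smallest n reaching 80%, for assumed values of r:

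| r | 0.5 | 0.6 | 0.7 | 0.75 | 0.8 | 0.9 | 1.0 |
|---|---|---|---|---|---|---|---|
| n | 10 | 14 | 18 | 20 | 23 | 28 | 34 |

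So 22 is attainable but cannot be confirmed. Other methods also reach a total of 22, for example a two-sample comparison with SD equal to 0.4 of mean pain (11 per arm). The method behind 22 is therefore not identifiable.

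**2. Size of the 20-versus-22 gap, if 22 is the minimum n for a paired t-test.** Solving power(n, d) = 0.80 gives d = 0.6264 at n = 22, 0.6428 at n = 21 and 0.6604 at n = 20. If 22 suffices and 21 does not, d lies between 0.6264 and 0.6428, so r lies between 0.5/0.6428 = 0.778 and 0.5/0.6264 = 0.798.

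At n = 20:
- d = 0.6264: noncentrality 0.6264 × √20 = 2.80, power 75.7%.
- d = 0.6428: noncentrality 0.6428 × √20 = 2.87, power 77.8%.

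The shortfall is 2 to 4 percentage points. Equivalently, 80% power at n = 20 needs a reduction of 0.6604 × 0.778 = 51% to 0.6604 × 0.798 = 53%, instead of 50%. If 22 governs, there is no shortfall.

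**3. Unranked tests at 0.05.** The SAP lists four variables. Assume one laser-versus-sharp test for each and no true difference in any:
- fully correlated tests: 5%;
- independent tests: 1 − 0.95⁴ = 1 − 0.8145 = 18.5%.

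The SAP does not state the number of tests. With independence, two tests would give 9.8%, three 14.3% and five 22.6%.

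**4. The two documents side by side.**

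| | Protocol | SAP |
|---|---|---|
| Number | 20, pilot | 22 needed for 80% power on pain |
| Primary endpoint | bioburden | none named |
| Pain | secondary | listed first; sole basis of power |
| Test for continuous data | two-sample t | paired t |
| Significance level | none stated | 0.05 for every analysis |

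**The case against.** The strongest reply is that nothing is flatly contradicted. The protocol ranks the endpoints, the SAP does not re-rank them, and both carry the same trial number, so pain presented as the main result would be visible to anyone who compared the two. The SAP says what number a pain assumption would need; it does not set an enrolment target. A declared pilot need not be powered for bioburden, and the pilot rationale discloses that choice.

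Much of this stands. A reader might infer that the SAP has replaced bioburden with pain as primary; its text does not say so. A reader might infer that the trial is underpowered or that 22 is miscalculated. The first depends on 20 governing and on an unidentified sizing method, and the second cannot be tested without an SD. Nor is 18.5% the trial's error rate: it needs one test for each of four variables, independence, and no account taken of the protocol's ranking.

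What the reply does not remove is that the later document fixes the tests and threshold and omits the ranking. The pilot rationale explains the 20; it does not explain a separate 22 or a blanket significance rule.

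**Conclusion.** The point holds as a failure to carry the protocol's primary endpoint into the SAP, together with a smaller unexplained difference in numbers. The textual facts are certain. The main consequence is a risk in presentation: the pain-only power statement and the unranked 0.05 rule leave room to lead with pain beside a null bioburden result.

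The figures are conditional. The range of 5% to 18.5% assumes one test for each of the four variables. The power of about 76–78% assumes both that 20 governs and that 22 was the minimum for a paired t-test. On either reading the difference between 20 and 22 is minor for a pilot. The matter is worth correcting because correction needs only wording.

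**What to change.** Add one dated note to the SAP, stating whether outcome data had been seen when it was written.

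1. Name the laser-versus-sharp bioburden contrast as the single primary test, as the protocol ranks it, at the SAP's two-sided 0.05 and with its paired analysis, and say that this supersedes the protocol's two-sample t-test. If the primary endpoint has changed, document and date the change instead. Label the other p-values, including pain, secondary or supportive.
2. Label the statement of 22 patients for 80% power as concerning pain, and say which number governs. If 20 governs, restate the pain power for 20 from the inputs that produced the 22 (about 76–78% if 22 was the minimum n for a paired t-test).
3. Report the bioburden difference with a 95% confidence interval, so that a null result can be read without a prior power figure.

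The cost is wording only, with no added enrolment. The downside is a slightly less favourable stated power if 20 governs, and a pain result that is reported as secondary even if it is significant.

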The laser provides precise control over the depth of ablation per pass, ranging from twenty five to two hundred microns. Ablation depth is tunable in twenty five-micron increments. The laser system handpiece allows the laser beam to be scanned to form two-dimensional spots onto the pattern size. The range of the pattern size is 0.64 - 9.00 centimeters squared. The handpiece scanner provides complete and uniform application of the laser energy. This application will cover forty percent of the surface within the scanned pattern. An aiming beam, displayed as a red square on the intended treatment surface, allows the clinician to visualize the treatment area. The laser energy will be delivered inside this red square. The adjoining scans will be delivered without gaps or overlaps to ensure even treatment.

Protective eye shields to safeguard against laser light exposures will be provided to the subjects and personnel in treatment room. The eye shields will remain in place until after the completion of the laser treatment. The thermal destruction of tissue creates a smoke by-product. A smoke evacuator attached to the laser handpiece will immediately remove any smoke generated throughout the laser treatment. This removal will prevent the smoke and debris from irritating the ulcer bed.

Laser ablation will be continued until the slough tissue is completely removed. Patient pain and pinpoint bleeding will represent the clinical endpoint of laser debridement. Pinpoint bleeding signifies the laser energy approaching the healthy underlying tissue. Laser debridement will be administered to only slough tissue and ulcer edges. Healthy granulation tissue in the ulcer bed will not be laser treated. After the completion of the laser debridement procedure, sterile gauze will be used to gently clean the ulcer bed to remove any remaining debris.

STUDY SCHEDULE

Screening and Enrollment (Study Week One):

- Obtain signed Informed Consent Form
- Review medical history to determine eligibility
- Perform medical examinations needed to determine eligibility

- Collect ulcer measurements and photos
- Randomize patients to treatment groups
- Provide subjects instructions needed for study participation
- Immediately proceed to the Treatment

Treatment (Study Week One):

1. Before debridement procedure:
 - Record VAS pain score, Present Pain Intensity, and Brief Pain Inventory
 - Collect ulcer photos and measurements
 - Collect biopsies
2. Apply anesthetic

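### For qPCR bacterial load the SAP gives only means (SD) and a paired t-test: no scale, no statement of which quantity is paired, and no period term

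*SAP*

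**What the plan says.** The protocol synopsis gives the primary endpoint as "Comparison of the two treatment modalities to reduce bioburden", measured by qPCR. Its study schedule has the instruction "Collect biopsies" before and after the procedure, in week one and again at the week two crossover visit. Each patient therefore has four measurement times. The number of biopsies at each time is not stated.

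The SAP (Methods) lists "pre- and post-debridement bacterial loads" among its analysis variables. Its Statistical Analysis paragraph covers all continuous variables in one line: "Descriptive analyses include means (standard deviation). A paired t-test was planned to evaluate continuous data". Nothing further is said about bacterial load. The SAP labels no variable as primary, and its only sample-size statement is about pain: "The a priori power analysis presumes a 50% reduction in patient-reported pain".

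The protocol synopsis has a different test: "Treatment effectiveness will be assessed by a two-sample t-test comparing the evaluation criterion at the two study intervals". It justifies the number of subjects with "This is a pilot study to determine treatment feasibility and efficacy".

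**The concern.** A paired t-test needs one number per patient per modality, and here there are two times per visit and no rule for combining them. The test could be run on post-debridement load or on the change from before to after, and on raw, percent or log10 values. These choices can give different answers on the same data.

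Scale matters because a reduction in bacterial load is naturally multiplicative. As an invented example, a fall from 10^7 to 10^6 is a raw change of 9,000,000 and a log10 reduction of 1. A fall from 10^5 to 10^3 is a raw change of only 99,000 but a log10 reduction of 2. On the raw scale the patients with the highest loads dominate both the mean and the SD.

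The protocol does not close the gap. Its two-sample test conflicts with the SAP, ignores the pairing, and can be read as comparing weeks instead of modalities.

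A secondary matter is that the second treatment falls on a wound already debrided (in one sequence the laser session is "followed by a single sharp debridement session one week later"), yet no period term is planned.

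**Working it through.** **The plan's own figure.** The 22 patients in the SAP are for pain, with no SD given, so the figure can be neither confirmed nor refuted. A paired t-test with n = 22 has 80% power at a standardised difference of 0.626. A 50% reduction matches that if the SD of the paired difference is 0.5/0.626 = 0.80 of the control mean. This says nothing about bacterial load.

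**Assumed model.** The documents give no mean, SD or effect for load. Take log10 pre = patient + visit + assay error. Take log10 post = the same patient and visit terms − base reduction (0.5 or 1.0) − extra laser effect + new assay error. N = 20 (protocol), 10 per sequence, two-sided α = 0.05 (SAP). SDs are written patient/visit/assay in log10 units.

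**Log10 change, exact.** Patient and visit terms cancel within a visit. The laser-minus-sharp difference in change has variance 4 × assay variance. At assay SD 0.4 this is 4 × 0.16 = 0.64, so the SD is 0.8. For an effect of 0.5 the noncentrality is 0.5 × √20 / 0.8 = 2.80. Power is 75.5% on 19 df, and 75.3% on 18 df with a period term. At N = 22 it is 79.8% without the period term.

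**Log10 post-load.** The variance of the paired difference is 2 × (visit variance + assay variance). At 0.5/0.5/0.4 this is 2 × (0.25 + 0.16) = 0.82, larger than 0.64, and power is about 65%. Change is therefore the more precise log10 reading only when visit variance exceeds assay variance. At 0.5/0.2/0.4 the post-load variance is 2 × (0.04 + 0.16) = 0.40, and post-load wins, 92% against 75%.

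**Power by reading of the SAP** (simulation for the raw readings):

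| Assumed loads | Raw change | Raw post | Log10 change |
|---|---|---|---|
| Lognormal 0.5/0.5/0.4, effect 0.5 | 2-4% | 18% | 75% |
| Lognormal 0.3/0.2/0.2, effect 0.4 | 4-12% | 86-87% | 99% |
| Gamma, CV 0.8/0.6/0.5, effect 0.4 | 9% | 70% | 95% |
| Additive normal, mean 100, SD 15/10/8, base reduction 30, extra 8 | 57% | 47% | 59% |

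**Null rejection if the reading is chosen afterwards.** Consider lognormal loads at 0.3/0.2/0.2, 0.5/0.5/0.4 and 1.0/0.5/0.4. The chance that raw change or log10 change gives p < 0.05 is about 6-8%. If raw and log10 post-load are also allowed, the chance that any of the four does is 10-13%.

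**Period (secondary).** Use 0.5/0.5/0.4, effect 0.5, and a 0.5 log10 week 2 shift in post-load only. With 10:10 sequences the estimate is unbiased, but power is 62% without the period term and 75% with it. With 13:7 the bias is 0.5 × (13 − 7)/20 = 0.15, so the estimate becomes 0.65 or 0.35 depending on the direction of the shift, and null rejection is about 7%. With the term it is 0.50 and 5%. Under simple randomisation of 20 patients, a split of 13:7 or worse has probability 0.263. The documents do not state the randomisation method.

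**The case against.** The strongest reply is that the protocol already points to the derived variable. Its objective, efficacy evaluation and primary endpoint all speak of reducing bioburden, and biopsies before and after each procedure fit a pre-to-post change. That stands. A reader might infer from the SAP alone that the paired quantity is wholly open and that the false-positive risk is 10-13%. The documents do not support stating that flatly. If change is taken as settled, the figure for raw against log10 is about 6-8%. Both ranges also require assumed SDs, lognormal loads and an analyst who tries every reading. What remains open is the scale of the change, and the SAP does not itself say that change is the paired quantity.

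The four readings counted above are not the only ones. Percent change is possible, and so is a pre-versus-post test within each modality, although the latter would not answer the between-modality endpoint.

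A reader might also infer that the readings usually disagree. That depends on the setting. At 0.5/0.5/0.4, effect 0.5, raw post-load and log10 change give different verdicts in 62% of simulated trials. At 0.3/0.2/0.2 with the same effect it is about 6%.

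Log10 change is one defensible choice, not the only one, and it loses power to log10 post-load when visit variance is low. The missing period term does not by itself bias a balanced trial. Finally, the pilot status and the power statement for pain limit how serious this is. All of that stands, but none of it supplies the missing specification.

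**Conclusion.** The concern holds in limited form. For the endpoint that the protocol calls primary, the SAP does not state the scale, does not say which quantity is paired, and plans no period term. The protocol's wording narrows the paired quantity to a probable pre-to-post change, but leaves its scale open and names a conflicting test.

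Under skewed, widely spread loads the consequence is large: power runs from about 2-4% on raw change to 75% on log10 change for the same true effect. With low spread or additive normal loads the scale matters less, although raw change can still do badly at low spread (4-12%). These sizes rest wholly on assumed SDs and effects.

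It would go too far to say that the SAP commits the sponsor to raw values, since it is silent on scale, or that the primary result would be invalid. Omitting the period term costs only power when sequences are balanced, and can bias the estimate when they are not. For a pilot, this should be corrected but is not fatal.

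**What to change.** State in the SAP that the primary bioburden outcome is the log10 reduction (log10 pre minus log10 post) at each visit. Compare modalities by regressing each patient's week 1 minus week 2 difference in that reduction on sequence (+1 laser first, −1 sharp first). The intercept carries the period effect, and the sequence coefficient is laser minus sharp. Report 10 to the power of that coefficient, the ratio of fold reductions, with its 95% CI. Replace the protocol's two-sample t-test with this analysis.

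The cost is a few lines of text and one degree of freedom (75.5% to 75.3% power in the setting above). The data are already collected. There are two downsides:

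- If visit variance is below assay variance, log10 post-load has more power (92% against 75% in the setting above). Log10 post-load adjusted for log10 pre-load and period can be reported as an optional sensitivity analysis. It should not be primary, because the week 2 pre-load is measured after the first treatment.
- The model does not remove a carry-over that alters the week 2 reduction itself. If that reduction is 0.2 log10 smaller after laser, the estimate rises by 0.2/2 = 0.10, from 0.50 to 0.60. A carry-over that shifts the week 2 pre- and post-loads equally does cancel.

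A rule for loads below a detection limit would be a useful optional detail, but its absence is not part of this point.

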3. Perform debridement procedure
 - Record technique or laser settings used during treatment
4. After debridement procedure:
 - Collect ulcer photos
 - Record VAS pain score, Present Pain Intensity, and Brief Pain Inventory
 - Record bleeding assessment
 - Collect biopsies
 - Provide Standard of Care

Follow Up Visit (Study Week Two):

- Subjects cross over to other study group
 - Remove ulcer dressing
1. Before debridement procedure:
 - Record VAS pain score, Present Pain Intensity, and Brief Pain Inventory
 - Collect ulcer photos and measurements
 - Collect biopsies
 2. Apply anesthetic
 3. Perform debridement procedure
 - Record technique or laser settings used during treatment
 4. After debridement procedure:
 - Collect ulcer photos
 - Record VAS pain score, Present Pain Intensity, and Brief Pain Inventory
 - Record bleeding assessment
 - Collect biopsies
 - Provide Standard of Care

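### Bioburden is measured before debridement at both visits but neither planned t-test uses it as a covariate; an estimated baseline slope may give a more precise laser-sharp comparison at almost no cost.

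*SAP*

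**What the plan says.** The SAP (Statistical Analysis) gives one rule for all continuous variables: "A paired t-test was planned to evaluate continuous data". Its Methods section lists "pre- and post-debridement bacterial loads" among the analysis variables. It does not say whether the test is run on post-debridement loads, on reductions, or pre against post within a treatment, nor on what scale.

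The protocol synopsis sets the primary endpoint as "Comparison of the two treatment modalities to reduce bioburden as determined by quantitative polymerase chain reaction (PCR) analysis, DNA sequencing" and its primary analysis as a "two-sample t-test comparing the evaluation criterion at the two study intervals". The Study Schedule has the entry "Collect biopsies" both before and after the procedure in week one. It repeats both entries in week two, where the visit opens with "Subjects cross over to other study group". A pre-debridement load is therefore available for each treatment in each patient.

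Neither document names a covariate, a period term or a sequence term. The protocol plans 20 patients and the SAP 22; the SAP's power statement concerns pain, not bioburden.

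**The concern.** A t-test has no place for a covariate, so the way the outcome is formed decides how the starting load is used.

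- **Paired t-test on log reductions.** The full pre-debridement value is subtracted, so the slope is fixed at 1. Noise specific to each pre-debridement biopsy enters the treatment difference, as does any between-visit change that does not carry into the post value. A load shift that carries fully into the post value cancels.
- **Paired t-test on post loads alone.** The slope is fixed at 0 and the baseline is ignored.

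Estimating the slope from the data is, in large samples, at least as efficient as either choice. What is at stake is precision on the protocol's primary endpoint in a trial of about 20 patients: a wider interval than necessary and a greater chance of missing a real laser-sharp difference.

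**Working it through.** **The plan's own figure.** The SAP's 22 patients (80% power, two-sided 0.05) cannot be confirmed or refuted, because no pain mean, SD or within-patient correlation is given. Solved backwards for a paired t-test with 21 df, 22 patients imply a standardised effect d = 0.626. With a 50% reduction this needs an SD of the paired difference of 0.5/0.626 = 0.80 of the mean pain score. The value d = 0.626 is borrowed below only as a reference point. At 20 patients the same d gives 75.7% power.

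**Assumptions.** For each patient let X be the laser-minus-sharp difference in log10 pre load and Y the same difference in log10 post load. X and Y have equal variance σ² and correlation r. Mean pre loads are equal, and there is no period or carry-over effect. None of these values is in the documents, so r is varied.

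**Variances.**

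- Post loads: Var(Y) = σ²
- Reductions: Var(Y − X) = 2(1 − r)σ²
- Adjusted: residual variance of Y given X = (1 − r²)σ²
- Adjusted relative to reductions: (1 − r²)/[2(1 − r)] = (1 + r)/2
- Adjusted relative to post loads: 1 − r²

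For the estimated slope, the variance is inflated by about 1 + 1/(N − 4), which is 1.0556 at N = 22, and the test has N − 2 df.

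**Example, N = 22, r = 0.5.** Both ratios equal 0.75. With inflation, 0.75 × 1.0556 = 0.792. The effective d is 0.626/√0.792 = 0.704, and the noncentrality is 0.704 × √22 = 3.30 on 20 df. Power is 88.1%, against 80% unadjusted.

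**Power of the adjusted analysis at N = 22, each comparator set to 80%.**

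| r | against reductions | against post loads |
|---|---|---|
| 0 | – | 78% |
| 0.2 | – | 79% |
| 0.3 | 92% | 81% |
| 0.5 | 88% | 88% |
| 0.7 | 84% | 97% |
| 0.8 | 82% | – |
| 0.9 | 80% | – |

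The two columns are calibrated separately, so they should be read down and not across. The break-even points follow from the ratios. Against reductions at r = 0.9, 0.95 × 1.0556 = 1.003. Against post loads at r = 0.2, 0.96 × 1.0556 = 1.013.

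At N = 20, from 75.7%, adjusted power against reductions is 89.0%, 84.3%, 79.6% and 77.3% at r = 0.3, 0.5, 0.7 and 0.8.

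**All three analyses on one scale.** With the effect fixed so that post loads have 80% power at N = 22, simulated power (post / reductions / adjusted) is about 80/51/78% at r = 0, 80/80/88% at r = 0.5 and 80/95/97% at r = 0.7. Adjustment is best, or within about 2 points of best, at each of these.

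**Checks.** In 40,000 simulated trials at N = 22 and r = 0.5, power was 80.0% for reductions and 88.2% adjusted; type I error was 5.1% and 4.9%. With a sequence term added, adjusted power was 87.8% at N = 22 and 83.9% at N = 20. That term costs up to about 0.5 points.

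**The case against.** The strongest reply is that the endpoint is itself a reduction, so the starting load is already subtracted. A reader might infer that every week-to-week difference in starting load stays in the error. The documents do not support that: on the log scale a shift that persists into the post value cancels. What stands is narrower, namely biopsy-specific noise and changes that do not carry over.

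A reader might also infer that the two visits start from different loads because the ulcer was debrided a week earlier. That is plausible, but neither document gives any load or regrowth data. A systematic shift at week two would be a period effect, which a sequence term handles, and is not in itself a reason for a covariate.

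Nor do the documents show that power is lost. With no r to go on, the gain against reductions disappears at r = 0.9, and against post loads adjustment costs 1 to 2 points at r between 0 and 0.2.

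It is also only one reading that the primary comparison is a paired t-test. The SAP names no primary endpoint and the protocol names a two-sample test. The absence of a covariate holds under either, but the power figures here apply to the paired test only. The conflict and the undefined outcome need settling at the same time.

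Finally, the week-two baseline is measured after the first treatment and may carry its effect. This is a real limit on the adjusted model. Reductions use the same baseline with full weight and do not avoid it; post loads alone do not use it.

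**Conclusion.** The point holds as a cheap improvement in precision, not as an error of validity. Neither planned test uses the pre-debridement load as a covariate, although it is scheduled at both visits. At N = 22, with the comparator at 80% power, the change from estimating the slope ranges from about +12 points (r = 0.3) to none (r = 0.9) against reductions. Against post loads it ranges from about −2 (r = 0) to +17 points (r = 0.7). At r = 0.5 it is about 8 points either way.

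These sizes rest on assumed r, equal pre and post variances, no period or carry-over effect, and an 80% target that the SAP states for pain only. The documents do not fix where in this range the trial lies. That uncertainty is the argument for estimating the slope: each fixed choice does poorly at one end of the range, and the estimated one is never far from the better of the two.

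**What to change.** In the SAP's Statistical Analysis section, define the bioburden comparison as a regression, one row per patient. The outcome is the laser-minus-sharp difference in log10 post-debridement load. The regressors are the same difference in log10 pre-debridement load, left uncentred so that the intercept refers to equal starting loads, and a sequence term coded −1/2 and +1/2. Report the intercept as the adjusted laser-minus-sharp difference with its 95% CI. State that this replaces both the paired and the two-sample t-test for this endpoint.

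A model with fixed patient effects, period, treatment and visit baseline gives the same estimate. A model with a random patient effect and raw visit baselines does not, because its slope mixes between-patient and within-patient relations; the patient-mean baseline would have to be added. In simulations at N = 22 with an assumed within-patient slope of 0.3 and a strong between-patient relation, that model's mean slope was about 0.7 against 0.3 for the difference regression. The treatment estimates lay 0.07 to 0.08 apart on average.

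Keep the paired t-test on log reductions as a sensitivity analysis. Show adjusted and unadjusted estimates side by side, with a note that the week-two baseline follows the first treatment.

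The cost is SAP wording, one degree of freedom for the slope and one for sequence, and little or no gain at some values of r. No new biopsies, visits or patients are needed.
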